#### 8.1.1 Other Names

VENCLEXTA™, ABT-199, A-1195425.0, GDC-0199, RO5537382

#### 8.1.2 Description

Structural Formula:	
Molecular Formula:	C 45 H 50 ClN 7 O 7 S
Molecular Weight:	868.44 kDa

#### 8.1.3 Mechanism of Action

Venetoclax is a novel, orally available small molecule Bcl-2 family protein inhibitor that binds with > 500-fold higher affinity to Bcl-2 and with lower affinity to other Bcl-2 family proteins Bcl-XL and Bcl-w. Overexpression of anti-apoptotic Bcl-2 family proteins is associated with increased resistance to chemotherapy, and antagonism of the action of these proteins might enhance response to such therapy and overcome resistance. Anti-apoptotic Bcl-2 family members are associated with tumor initiation, disease progression, and drug resistance, making them compelling targets for antitumor therapy.

#### 8.1.4 Pharmacokinetics

Half-life:	~26 hrs
Distribution:	Highly bound to plasma protein
Metabolism:	Predominantly by CYP3A4/5; M27 is a major metabolite
Excretion:	>99.9% feces, < 0.1% urine

#### 8.1.5 Human Toxicity

See [Section 6.1](#).

#### 8.1.6 Formulation

Venetoclax tablets will be used for this study.

#### 8.1.7 Storage

Store at 15° to 25 °C.

### **8.1.8 Handling and Dispensing**

The investigator should ensure that investigational agent venetoclax is stored in accordance with the environmental conditions (temperature, light, and humidity) as per product information and the Investigator Brochure and per local regulations.

The investigational product must be dispensed only from official study sites by authorized personnel according to local regulations.

If concerns regarding the quality or appearance of the study drug arise, the study drug should not be dispensed and contact AbbVie immediately.

### **8.1.9 Administration**

See [Section 5.4.1](#)

### **8.1.10 Supplier**

The investigational venetoclax will be supplied free of charge by AbbVie.

### **8.1.11 Ordering**

Sites will place orders for venetoclax via the AbbVie drug portal. The timing for initial and resupply will be the same.

Sites should place orders a week in advance of the shipment.

### **8.1.12 Accountability**

The investigator, or a responsible party designated by the investigator, must maintain a careful record of the inventory and disposition of the agent (investigational or free of charge) using a drug accountability log.

It is the responsibility of the investigator to ensure that investigational product is only dispensed to study participants.

### **8.1.13 Destruction and Return**

The investigator is responsible for keeping accurate records of the clinical supplies received from AbbVie or designee, the amount dispensed to participants, and the amount remaining at the conclusion of the trial.

Any unused agent at the end of the study, expired agent, and damaged agent will be destroyed according to applicable federal, state, local and institutional guidelines and procedures. **Prior to the destruction of venetoclax, the DCC should be notified and an acknowledgement to proceed from the DCC should be received.**

Destruction will be documented in a drug accountability log.

## **8.2 Romidepsin**

### **8.2.1 Other names**

Istodax®, Romidepsin for injection, FK228, depsipeptide

## 8.2.2 Description

Structural Formula:	
Molecular Formula:	C 24 H 36 N 4 O 6 S 2 •CH 4 O
Molecular Weight:	572.74 kDa

## 8.2.3 Mechanism of Action

Romidepsin is a unique bicyclic depsipeptide originally isolated from *Chromobacterium violaceum* strain 968. Romidepsin is an antineoplastic agent that has been identified as a novel HDAC inhibitor. Romidepsin has been shown to induce hyperacetylation of histones and other nonhistone protein species resulting in a variety of phenotypic changes, induction of the upregulation of gene transcription, G1 and G2/M arrest of the cell cycle, morphological reversion of transformed cells, cell growth inhibition, apoptotic cell death, and inhibition of angiogenesis. In vitro, romidepsin causes the accumulation of acetylated histones, and induces cell cycle arrest and apoptosis of some cancer cell lines with IC50 values in the nanomolar range. The mechanism of the antineoplastic effect of romidepsin observed in nonclinical and clinical studies has not been fully characterized.

## 8.2.4 Pharmacokinetics

Half-life:	~3 hrs
Distribution:	Highly bound to plasma protein
Metabolism:	Predominantly by CYP3A4/5
Excretion:	accumulates in bile and excreted in feces

## 8.2.5 Human Toxicity

See [Section 6.2](#)

## 8.2.6 Formulation

Romidepsin Injection is a sterile, clear colorless to pale yellow solution and is supplied in single-dose vials. Each mL contains romidepsin 5 mg, povidone 10 mg, DL-α-pha-tocopherol 0.05 mg, dehydrated alcohol 157.8 mg (20.1% v/v) and propylene glycol 828.8 mg.

## 8.2.7 Storage

20° to 25° C, excursions permitted between 15° to 30° C. (See [USP Controlled Room Temperature](#).)

## 8.2.8 Handling and dispensing

Romidepsin should be handled in a manner consistent with recommended safe procedures for handling cytotoxic drugs.

Romidepsin must be reconstituted with the supplied diluent and further diluted with 0.9% Sodium Chloride Injection, USP before intravenous infusion.

**8.2.9 Administration**

See [Section 5.4.2.](#)

**8.2.10 Supplier**

Romidepsin will be available through commercial supply.

## 9.0 CORRELATIVE/ SPECIAL STUDIES

---

### 9.1 Tumor Tissue Studies

An overview of collection, processing, and analysis details are shown in [Table 9.1](#).

**Table 9.1. Overview of Tumor Tissue Studies**

Tissue Type	Timepoint of collection	Planned Future Analaysis
Formalin fixed archived biopsy	Baseline	
 
• BCL2 expression status and correlation with response
 
• Changes in gene expression
 

Fresh tissue	
 
• Baseline
 
• Optional: During Cycle 1 or Cycle 2
 
	

#### 9.1.1 Timepoints of Collection

- *Baseline tissue:*
  - *Fresh tissue (after informed consent):* If a standard of care fresh core or excisional biopsy of the tumor lesion is to be performed, attempts should be made to take extra tissue for research.
  - *Formalin-fixed tissue:* Archived biopsy tumor tissue should be submitted.
  - *During Cycle 1 or Cycle 2 (optional):* Submit fresh core or excisional biopsy of the tumor lesion for research if the participant is willing.

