#### 3.1 Inclusion Criteria

Informed Consent and Willingness to Participate

- 1. Documented informed consent of the participant and/or the legally authorized representative
- 2. Be willing to provide tissue (See [Section 9.1](#))

Age and Performance Criteria

- 3. Age  $\geq$  18 years
- 4. ECOG  $\leq$  2

Nature of Illness and Treatment History

- 5. Resolution of all acute toxic effects of prior therapy or surgical procedures to CTCAE Grade  $\leq$  1 (except alopecia).
- 6. Failed at least 2 prior systemic therapies. For ALCL histologies this must include failure or intolerable side effects of brentuximab vedotin
- 7. Histologically confirmed PTCL as defined by the WHO criteria 2016, excluding CTCL. Transformed mycosis fungoïdes is allowed.
- 8. Measurable disease defined as:
  - CT/MRI/ or PET scan, with at least one nodal site of disease which is 1.5 cm in longest dimension, and/or spleen  $>$  13 cm in vertical length, and/or diffuse enlargement of liver with or without focal nodules (Lugano 2014). Extra nodal sites with biopsy proven abnormal lesions are allowed including skin.
  - Patients with only bone marrow involvement will be acceptable.
- 9. Prior stem cell transplant allowed
  - If allogeneic HCT must have recovered from acute toxicity
  - Cannot have active acute or chronic GvHD and must be off immunosuppressive therapies

Clinical Laboratory Criteria (To be performed within 14 days prior to Day 1 of protocol therapy)

 10. ANC $\geq$ 1,000/mm  NOTE: Growth factor is not permitted within 7 days of ANC assessment unless cytopenia is secondary to disease involvement. Exception: Unless documented bone marrow involvement by lymphoma	ANC:	Date:
 11. Platelets $\geq$ 30,000/mm  NOTE: Platelet transfusions are not permitted within 7 days of platelet assessment unless cytopenia is secondary to disease involvement. Exception: Unless documented bone marrow involvement by lymphoma	Plts:	Date:

12. Total bilirubin $\leq 1.5 \times$ ULN ( $\leq 3 \times$ ULN for Gilbert's Syndrome or documented hepatic involvement by lymphoma)	ULN: Bil:	Date:
13. AST $\leq 3 \times$ ULN If hepatic involvement by lymphoma: AST $\leq 5 \times$ ULN	ULN: AST:	Date:
14. ALT $\leq 3 \times$ ULN If hepatic involvement by lymphoma: ALT $\leq 5 \times$ ULN	ULN: ALT:	Date:

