- r. *Adverse event (AE)* will be assessed using CTCAE v.5.0. SAEs related to study procedures will be recorded and reported from time of informed consent until Day 1 of protocol therapy.
- s. Toxicities AE recording and reporting will continue until the completion of [Safety Follow-up period](#) or until resolution or stabilization of any reportable AE occurring during Safety Follow-up.
- t. *Women of child bearing potential*: Pregnancy serum or urine test.
- u. *Screening laboratory assessments* to be performed within 14 days prior to start of protocol therapy.
- v. *Serum chemistry* panel to include: glucose, Blood Urea Nitrogen (BUN), creatinine, uric acid, total protein, albumin, magnesium, bicarbonate, calcium, inorganic phosphorous, sodium, potassium, chloride, total CO2, total bilirubin, alkaline phosphatase, ALT, AST, and LDH.
- w. *TLS serum chemistry monitoring post-Day 1, Day 2, Day 3, Day 4, Day 5, Day 6, Day 7 and Day 8 dose* to include potassium, uric acid, phosphorus, calcium, and creatinine. **Monitoring times are:** predose, and post dose 6-8 hours

and 24 (+/- 2) hours. Next dose should not be administered until 24 h blood chemistry values are evaluated. See **Table 5.9.1.**

- x. CT/MRI imaging for PTCL at baseline.
- y. *Disease and response assessment:* Cycle 3 Day 1 (-7 days), then every 2 cycles (-7 days). CT scan may take place within 7 days prior to D1 but not after D1 of the cycle in question.
- z. FDG-PET scan will be performed at screening. Subsequent PET scans will not be needed until the EOT visit or disease progression, whichever comes first.
- aa. *Bone marrow biopsy/aspirate* that was performed within 120 days prior to Day 1 may serve as Screening assessment.
- bb. PTCL response (Lugano criteria). Refer to [Section 11.3](#) for details.
- cc. *TLS prophylaxis* to be initiated prior to protocol therapy within 72 hours as stated in [Table 5.9.1](#). Participants should receive continued TLS prophylaxis as clinically indicated.
- dd. Refer to [Section 5.3](#) for the treatment plan. Refer to [Section 6.2](#) for dose modification/ delay guidelines and [Section 5.9](#) for supportive care guidelines.
- ee. Romidepsin will be administered intravenously on Days 1, 8, and 15 of each cycle. A window is allowed for romidepsin infusion visits (within  $\pm 3$  days of day 1 and within +3 days of days 8 and 15)
- ff. *Pill Diary* will be given to the participant and will be reviewed for adherence. See [Appendix G](#).

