- gg. *Baseline tissue:* Archival tissue of a biopsy and if applicable, fresh core or excisional biopsy of a tumor lesion at time of standard of care biopsy.
- hh. *Optional:* Research fresh core or excisional biopsy of the tumor lesion only if the participant is willing.

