All measurable lesions up to a maximum of 2 lesions per organ and 5 lesions in total, representative of all involved organs, should be identified as target lesions and recorded and measured at baseline. Target lesions should be selected on the basis of their size (lesions with the longest diameter), be representative of all involved organs, but in addition should be those that lend themselves to reproducible repeated measurements. It may be the case that, on occasion, the largest lesion does not lend itself to reproducible measurement in which circumstance the next largest lesion which can be measured reproducibly should be selected. A sum of the diameters (longest for non-nodal lesions, short axis for nodal lesions) for all target lesions will be calculated and reported as the baseline sum diameters. If lymph nodes are to be included in the sum, then only the short axis is added into the sum. The baseline sum diameters will be used as reference to further characterize any objective tumor regression in the measurable dimension of the disease.

- Non-target lesions

All other lesions (or sites of disease) including any measurable lesions over and above the 5 target lesions should be identified as non-target lesions and should also be recorded at baseline. Measurements of these lesions are not required, but the presence, absence, or in rare cases unequivocal progression of each should be noted throughout follow-up.

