## APPENDIX C-2: PTCL RESPONSE CRITERIA

Response	Site	CT-Based Response	PET-CT Based Response
Complete Response		Complete radiologic response (all of the following)	Complete metabolic response (even with a persistent mass)
	Lymph nodes and extralymphatic sites	
Target nodes/nodal masses must regress to <math>\leq 1.5</math> cm in longest diameter.
 
No extralymphatic sites of disease.
	
Score <math>\leq 3^*</math> with or without a residual mass on 5-point scale†.
 
It is recognized that in Waldeyer's ring or extranodal sites with high physiologic uptake or with activation within spleen or marrow (e.g., with chemotherapy or myeloid colony-stimulating factors), uptake may be greater than normal mediastinum and/or liver. In this circumstance, complete metabolic response may be inferred if uptake at sites of initial involvement is no greater than surrounding normal tissue even if the tissue has high physiologic uptake.

	Nonmeasured lesion	Absent	Not applicable
	Organ enlargement	Rgress to normal	Not applicable
	New lesions	None	None
	Bone marrow	Normal by morphology; if determinate, IHC negative	No evidence of FDG-avid disease in marrow
Partial Response		Partial remission (all of the following)	Partial metabolic response
	Lymph nodes and extralymphatic sites	
<math>\geq 50\%</math> decrease in SPD of up to 6 target measurable nodes and extranodal sites
 
When a lesion is too small to measure on CT, assign 5 mm X 5 mm as the default value
 
When no longer visible, 0 X 0 mm
 
For a node <math>> 5</math> mm X 5 mm, but smaller than normal, use actual measurement for calculation
	
Score 4 or 5† with reduced uptake compared with baseline and residual mass(es) of any size
 
At interim, these findings suggest responding disease
 
At end of treatment, these findings indicate residual disease

Response	Site	CT-Based Response	PET-CT Based Response
	Nonmeasured lesion	Absent/normal, regressed, but no increase	Not applicable
	Organ enlargement	Spleen must have regressed by > 50% in length beyond normal	Not applicable
	New lesions	None	None

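### An optional research excision in Cycle 1 or 2 can remove a target lesion before the first response CT, and no scoring rule excepts it, so a PR can be recorded without drug effect when that lesion is at least half of baseline SPD

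*Combined protocol and SAP*

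**What the plan says.** **Biopsy.** Section 9.1.1, for the optional sample in Cycle 1 or Cycle 2: "Submit fresh core or excisional biopsy of the tumor lesion for research if the participant is willing". Footnote hh of the study calendar (Table 10.0) repeats it: "Research fresh core or excisional biopsy of the tumor lesion only if the participant is willing". Neither says which lesion may be taken.

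**Timing and modality.** Footnote y puts the first response assessment at Cycle 3 Day 1, up to 7 days earlier but not later. Footnote z says of PET: "Subsequent PET scans will not be needed until the EOT visit or disease progression, whichever comes first". The first on-treatment assessment is therefore normally by CT.

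**Which lesions are targets.** Inclusion criterion 8 in Section 3.1 is met by disease "with at least one nodal site of disease which is 1.5 cm in longest dimension". Appendix C-1 selects as targets "All measurable lesions up to a maximum of 2 lesions per organ and 5 lesions in total".

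**Scoring.** The CT criterion for PR in Appendix C-2 is at least a 50% "decrease in SPD of up to 6 target measurable nodes and extranodal sites", with no new lesions and no increase in nonmeasured lesions. For a lesion that cannot be seen: "When no longer visible, 0 X 0 mm". Neither appendix mentions a lesion removed by surgery.

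**Use of the result.** ORR is the Phase 2 primary endpoint. Section 12.1.2 stops at 0 responses in 7 and declares the regimen promising at 4 or more in 18.

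**The concern.** Each rule is ordinary alone. Together they let a research procedure change the measurement on which the primary endpoint rests. A patient with one or two measurable nodes has all of them as targets, so an accessible node offered for excision is likely to be in the SPD. Once it is out, the next CT shows nothing there, and the only written instruction for that finding is to enter zero.

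For response scoring the error can only help the regimen. The decision rules are sensitive to single patients: one response among the first 7 passes the futility look, and the final cut is 4 responses.

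**Working it through.** **1. The plan's own design.** Inputs from Section 12.1.2: null 10%, alternative 30%, one-sided type I error 10%, power 80%, n1 = 7, continue if at least 1 response, n = 18, promising if at least 4 responses.

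P(promising | p) = sum over x = 1 to 7 of P[Bin(7, p) = x] × P[Bin(11, p) ≥ 4 − x]

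At p = 0.10:

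| x in Stage 1 | P(x) | P(at least 4 − x in the next 11) | Product |
|---|---|---|---|
| 1 | 0.3720 | 0.0896 | 0.0333 |
| 2 | 0.1240 | 0.3026 | 0.0375 |
| 3 | 0.0230 | 0.6862 | 0.0158 |
| 4 to 7 | 0.0027 | 1 | 0.0027 |

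The sum is 0.0893. At p = 0.30 the same formula gives 0.8000. The chance of stopping at 0 of 7 under the null is 0.9^7 = 0.478. A search over two-stage designs returns the same one (0/7, 3/18) as optimal, so the plan's figures reproduce.

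**2. When excision alone reaches PR.** Removing one of m equal target lesions cuts SPD by 1/m. The last column is the SPD shrinkage s that the remaining targets must show to reach PR, from (1 − 1/m)(1 − s) ≤ 0.5.

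| m | Fall in SPD from excision | PR size cut met by excision alone? | Shrinkage still needed in the rest |
|---|---|---|---|
| 1 | 100% | yes | none |
| 2 | 50% | yes, exactly at the cut | none |
| 3 | 33% | no | 25% |
| 4 | 25% | no | 33% |
| 5 | 20% | no | 37.5% |

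For example, two nodes of 3 × 2 cm give a baseline SPD of 12 cm². Excising one leaves 6 cm², a 50% fall. In general the excised lesion must be at least half of baseline SPD. With three or more equal targets, excision is not enough but lowers the true shrinkage needed from 50% to the value shown.

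**3. Effect on the decision if a fraction f of true non-responders is converted.** The documents give no biopsy uptake, so f is an assumption. At a true ORR of 10% the apparent rate is p = 0.10 + 0.90f, put into the formula of step 1. The expected number of false responders in 18 is 18 × 0.9 × f = 16.2f.

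| f | Apparent rate | Expected false responders | P(stop at 0/7) | P(declared promising) |
|---|---|---|---|---|
| 0 | 0.100 | 0 | 0.478 | 0.089 |
| 2% | 0.118 | 0.32 | 0.415 | 0.141 |
| 5% | 0.145 | 0.81 | 0.334 | 0.238 |
| 10% | 0.190 | 1.62 | 0.229 | 0.423 |

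**4. Exactly one false responder among the 18, true ORR 10% in the other 17.**
- In Stage 1, the futility look is always passed and 3 more responses are needed from 17: P[Bin(17, 0.1) ≥ 3] = 0.238.
- In Stage 2, subtract the paths that would have stopped at 0 of 7: 0.2382 − 0.4783 × P[Bin(10, 0.1) ≥ 3] = 0.2382 − 0.4783 × 0.0702 = 0.205.
- Weighted by position: (7 × 0.238 + 11 × 0.205)/18 = 0.218.

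**The case against.** **Several conditions must coincide.** The patient must accept an optional biopsy. It must be excisional and fall before the response CT. The lesion must be at least half of baseline SPD. There must be no new lesions and no increase in nonmeasured disease, and the patient must not have responded anyway. This stands. It limits frequency, and the documents support no particular rate.

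**Stronger readings that do not hold.**
- A reader might infer that any excised target counts as a response. Step 2 shows that it does not with three or more equal targets.
- A reader might infer that CR is as easily reached. CT-based CR also requires no extralymphatic disease, nonmeasured lesions absent, enlarged organs back to normal and a normal marrow, so it arises only if the excised lesion was essentially the whole disease.
- A reader might take one or two consenting patients in 18 and read off a type I error of 0.205 to 0.485, since two false responders give 0.378 to 0.485. Those figures are for false responders, not for excisions.

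**Target selection gives partial protection.** Appendix C-1 prefers targets that can be measured repeatedly and reproducibly, which would argue against a node already booked for excision. It does not cover a biopsy agreed after baseline.

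**The criteria might be read sensibly.** The CR rule speaks of nodes regressing, and the zero entry sits beside a small-lesion convention. The cited Lugano paper, not available here, or an experienced radiologist, might not treat a resected node as regression. That is possible, but the protocol's own tables leave it unsaid, and the one instruction for a lesion not seen points the other way.

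**Other checks would not catch it.** Section 12.5 refers to confirmed responses without defining confirmation, and an excised node stays absent on a repeat scan. The tissue form in Appendix F-2 offers only baseline and progression as time points.

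**Conclusion.** The gap is real and conditional. As written, the plan lets an on-treatment research excision produce a PR in the primary ORR when the lesion is at least half of baseline SPD and there are no new lesions and no increase in nonmeasured disease. In patients with more targets it can add to real shrinkage.

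Its size cannot be fixed from the documents. Under the assumed conversion range of 2% to 10% of true non-responders, the chance of declaring an inactive regimen promising (true ORR 10%) is 0.141 to 0.423, against 0.089 by design. A single false responder already gives 0.205 to 0.238, above the planned 10%. If few patients accept excision, the effect may be nil.

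Footnote gg is a lesser matter. Baseline fresh tissue is extra material from a biopsy done as standard of care, so the research plan does not cause that excision. It matters here only for scoring, when such a biopsy follows the baseline CT.

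**What to change.** 1. **Sampling.** In Section 9.1.1 and footnote hh, state that on-treatment research excisional samples are taken only from lesions not counted in the SPD. If no such lesion is accessible, the research sample is a core.
2. **Scoring.** In Appendices C-1 and C-2, state that any lesion excised after the baseline CT, including by a standard-of-care biopsy, is removed from both the baseline and the follow-up SPD and is never entered as 0 × 0 mm regression. Excision of the only measurable lesion is not a basis for CR or PR.
3. **Leave footnote gg as it is** on the choice of standard-of-care baseline biopsy; the scoring rule is enough there.

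The scoring rule needs a record of which lesion was taken and when, for which Appendix F-2 lacks a Cycle 1 or 2 option.

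**Cost.** A few sentences in an amendment. Some optional samples, which serve exploratory objectives only, will be cores and not whole nodes. If excision never creates a response, the design keeps its type I error of 0.0893 and power of 0.8000. That power has no slack, so a patient whose sole measurable lesion is removed and who therefore counts as a non-responder would take it slightly below 80%. The sampling rule keeps such cases rare.
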